The second baseline testing session (BV2) will occur in the Wake Forest University Department of Health and Exercise Science. During this visit, participants will undergo muscle function tests (expanded Short Physical Performance Battery (SPPB) test, Timed-Up-and-Go (TUG) test, fast 20-meter and 400-meter walk tests, and stair climb test), DXA scan (whole body, hip and spine), physical activity questionnaire (Community Healthy Activities Model Program for Seniors; CHAMPS), quality of life questionnaire (SF-12), disability questionnaires (Pepper Assessment Tool for Disability; PAT-D and Mobility Assessment Tool-short form; MAT-sf), and instructions will be provided for a dietary run-in (approximately 30 minutes). For the dietary run-in, all participants will be provided with and oriented to the Medifast® OuickStart Guide, sample meal plans, 3, one-day dietary trackers, a sampling of 12 Medifast Meal Replacement Products, 3, one-day Product Evaluation Forms, and asked to follow the Medifast 4 &2 &1 PlanTM for a three -day period occurring over the following week. Participants will be contacted by the study registered dietitian (RD) upon completion of the dietary run in period to assess their willingness and self-efficacy to adhere to the dietary protocol for the duration of the study (24 weeks). Participants who indicate that they are willing and able to follow the protocol will be randomized (RAND) to one of the 2 study interventions (high protein weight loss group vs. weight stable control group), with blocking stratified by gender, and treated in 5 successive waves (n=12-13 participants/group/wave). Randomization of the entire wave (n=24-26) will occur approximately 1 week prior to the start of intervention, and at this time the first monthly Medifast product order will be placed for participants randomized to the high protein weight loss group.

All assessments conducted at the BV1 and BV2 testing sessions will be repeated at two follow-up visits (FV1 and FV2), occurring during the last two weeks of active intervention (weeks 23-24). Lastly, a brief midpoint visit (MP; week 12) will occur for all participants, where only DXA and fast 400-meter walk tests will be performed.

Visit	Location of Visit	Sticht	WFU	WFU	WFU	Sticht	WFU
Code	Week Number	-3	-2	-1	0-24	23	24
SV1	Informed consent, review inclusion/exclusion criteria (including demographics and BMI)	Х					

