In addition to receiving dietary counseling, all participants randomized to the high protein weight loss group will attend behavioral counseling group classes led by the RD. These classes will be held bi-weekly for the duration of the study (with an additional phone call at week 1) to provide participants an opportunity to review specific questions and problems. Group counseling sessions will provide support and introduce new topics in behavioral weight control including self-monitoring, portion control, mindful eating, coping with negative thoughts related to overeating, eating at regular times, and stress management. Weight will be measured bi-weekly, at each class, to provide additional feedback and to increase motivation. Official study baseline and post-intervention weights will occur at weeks 0 and 24 of intervention, respectively. Additionally, participants will complete daily food logs which will be reviewed by the RD to verify compliance to the diet. If it is evident, either through inadequate body weight loss or diet records, that participants are not compliant with the diet, additional individual counseling sessions with the RD will be held to improve compliance. Also, at week 24, participants in this group will be asked to complete a program evaluation form to solicit feedback on overall weight loss program product satisfaction and desired future usage, as well as product quality and taste feedback and recommendations.

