Weight Stable Control Group – Participants randomized to the weight stable control group will be monitored bi-weekly by study staff (with an additional phone call at week 1) to ensure weight stability over the course of the study. Participants will be weighed on a bi-weekly basis and encouraged to maintain weight within $\pm 5\%$ of baseline. To promote compliance and retention, participants will also be invited to bi-weekly group educational sessions, where non-weight loss health related topics (including: What is Successful Aging?, Preventing and Delaying Disease and Dysfunction, Managing Medications Effectively, and Talking Effectively with Your Healthcare Provider), will be discussed by study staff. Lastly, if weight stable participants are able to attend 75% (i.e. 9 of 12) educational sessions, all baseline and follow-up testing sessions, and maintain weight stability over the course of the study (defined as less than a 5% differential between weight measured at week 0 and 24), they will be eligible to receive up to 3 months of Medifast MRPs along with a 30-60 minute RD-led dietary instruction session on how to follow the Medifast 4 & 2 & 1 Plan.

Methods for Study Assessments

The nature, purpose, and risks of all procedures and protocols will be explained to each participant prior to obtaining written consent. All examiners are trained in the standardized conduct of all assessments before data collection. Participants will be instructed to wear appropriate and comfortable clothing, and standardized written instructions will be provided prior to each study visit.

Study Measure(s)

- 1. Height, body mass, BMI, & waist circumference. **Height** without shoes will be measured to the nearest 0.1 centimeter using a stadiometer and **body mass** will be measured to the nearest 0.1 kilogram using a calibrated and certified balance beam scale. Height and body mass will be used to calculate **BMI**. **Waist circumference** will be measured to the nearest 0.1 cm with a Gulick-II spring-retractable steel tape.

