Data analyses: Regression diagnostics, residual plots, and exploratory analyses will be performed to find appropriate transformations for all variables to satisfy linearity, homogeneity of variances, and normality assumptions. Descriptive statistics consisting of frequency tables and percentages for categorical variables, and means, standard deviations, medians, and ranges for continuous variables will be tabulated and presented by intervention group and time point. Exact 95% confidence intervals (CIs) will be provided for the estimated proportions and approximate 95% CIs for estimated means. The primary outcome of the intervention effect on fast 400-meter walk gait speed will be analyzed using an ANCOVA model fit with the main effect of treatment arm and adjusted for baseline values of fast 400-meter walk gait speed. The primary test will be covariate-adjusted main treatment effect of the weight loss intervention compared to the control group, and we assume a Type I error rate of 0.05 for the two-sided alternative hypothesis. Secondary measures of body composition will be analyzed similarly, using baseline values of the particular body composition measure as a covariate in the outcome model. Other data including feasibility and compliance data collected in this study will be used to inform future studies of weight loss in older adults. All statistical analyses will be conducted assuming intent-to-treat so that participants will remain assigned to the initial randomization group regardless of treatment adherence, and participants who do not adhere or discontinue treatment will still be encouraged to provide outcomes data. Our group has past success in retaining participants by maintaining frequent contact with individuals who encounter barriers to participation and creatively accommodate and counsel, as necessary, to encourage the maximum degree of participation. To ensure the results are not overly influenced by missing data, a multiple imputation sensitivity analysis of the primary outcome will be performed using both baseline and post-randomization characteristics to inform the missing data imputation, assuming observations are missing at random.

Human Subjects Protection

Subject Recruitment Methods

We will recruit individuals using community-based recruitment strategies including mass and direct mailings and the local newspapers. We will also advertise in the VITAL newsletter (BG99-559) and participate in community outreach events.

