Confidentiality will be protected by collecting only information needed to assess study outcomes, minimizing to the fullest extent possible the collection of any information that could directly identify subjects, and maintaining all study information in a secure manner. To help ensure subject privacy and confidentiality, only a unique study identifier will appear on the data collection form. Any collected patient identifying information corresponding to the unique study identifier will be maintained on a separate master log. The master log will be kept secure, with access limited to designated study personnel. Following data collection, subject identifying information will be destroyed at the earliest opportunity (following a minimum of 3 years of record retention per the Wake Forest School of Medicine IRB policy), consistent with data validation and study design, producing an anonymous analytical data set. Data access will be limited to study staff, and also to Medifast Clinical Affairs personnel. Data and records will be kept locked and secured, with any computer data password protected. No reference to any individual participant will appear in reports, presentations, or publications that may arise from the study.

Data and Safety Monitoring

The principal investigator will be responsible for the overall monitoring of the data and safety of study participants. The principal investigator will be assisted by other members of the study staff, including the study physician, [name]. In addition, all project related data and safety will be reviewed biannually by the WFUSM's Older Americans Independence Center's (OAIC) independent Data Safety Monitoring Board (DSMB).

Reporting of Unanticipated Problems, Adverse Events or Deviations

Participants will be queried at bi-weekly intervention sessions for adverse events (AE). Events will be recorded on AE tracking forms and categorized based on severity (mild/moderate/severe), seriousness (yes/no), and relatedness to the study intervention (unrelated, possibly, probably, and definitely). Any unanticipated problems, including serious and unexpected adverse events, as well as deviations or protocol changes will be promptly reported by the principal investigator or project manager to the IRB, the WFUSM OAIC DSMB, and Medifast.

Use of biological samples by other investigators

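### The only stated adverse event query is at bi-weekly intervention sessions, so a participant who stops sessions is not scheduled to be asked again, and equal ascertainment by arm is not secured

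*Combined protocol and SAP*

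**What the plan says.** The rule is in the section Reporting of Unanticipated Problems, Adverse Events or Deviations: "Participants will be queried at bi-weekly intervention sessions for adverse events (AE"). Events go on tracking forms and are graded for severity, seriousness and relatedness.

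The sessions are described differently for the two arms under Study Interventions. In the weight loss arm, "all participants randomized to the high protein weight loss group will attend behavioral counseling group classes led by the RD", and weight is taken at each class. In the control arm, "Participants will be weighed on a bi-weekly basis and encouraged to maintain weight within" 5% of baseline, and separately "participants will also be invited to bi-weekly group educational sessions". Controls have a product reward, one condition of which is met "if weight stable participants are able to attend 75% (i.e. 9 of 12) educational sessions".

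The assessment visits are described under Participant screening, assessments and randomization. At midpoint, "a brief midpoint visit (MP; week 12) will occur for all participants, where only DXA and fast 400-meter walk tests will be performed". At the end, "All assessments conducted at the BV1 and BV2 testing sessions will be repeated at two follow-up visits (FV1 and FV2").

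On people who stop, Data analyses says that "participants who do not adhere or discontinue treatment will still be encouraged to provide outcomes data". It does not mention adverse events.

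**The concern.** The query is tied to a contact that participants can give up while staying in the trial. Someone who leaves the sessions, possibly because of an adverse event, may still come for the week-12 walk test and the final visits. No question is scheduled for them there. The plan follows such people for efficacy under intent-to-treat and states no equivalent for safety.

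The second issue is the arms. If the query takes place at the control arm's educational sessions, its opportunity depends on attendance at an optional event. If it takes place at weigh-ins, both arms have the same bi-weekly schedule. The protocol does not say which is meant.

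At stake is the completeness of the safety record. The Background gives lean and bone loss, disability and fracture as reasons why weight loss at this age is disputed. Potential Risks names falls, strains and joint injury from the performance tests, which are repeated at visits with no query listed. The primary gait-speed analysis is not affected.

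**Working it through.** The documents give no adverse event rate, attendance rate or adverse event analysis, so there is no figure of the plan's own to reproduce. The main check is to go through each described contact and see whether an adverse event query is listed.

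| Contact | Where described | Query listed? |
|---|---|---|
| Bi-weekly intervention sessions | Reporting of Unanticipated Problems, Adverse Events or Deviations | Yes |
| Week-1 phone call, both arms | Study Interventions | No |
| Bi-weekly weighing, both arms | Study Interventions; Table 2; Compliance and satisfaction | Not named, unless this is the session meant |
| Control educational sessions | Weight Stable Control Group | Not named, unless this is the session meant |
| Week-12 visit | Participant screening, assessments and randomization; Table 2 | No; limited to DXA and the 400-m walk |
| Week-23 and week-24 visits | Same | No; they repeat baseline assessments, which list none |
| Retention contact | Data analyses | No |

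Abnormal follow-up tests lead to medical referral, which is not an adverse event query. Prompt reporting to the IRB, the DSMB and the funder, and the biannual DSMB review, deal with events already known.

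For a person who stops sessions and still attends assessments, every remaining listed contact is therefore without a scheduled query.

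**Illustration of size.** Inputs from the Sample size paragraph are 62 per arm and 15% drop-out overall (0.15 × 62 = 9.3 per arm). Drop-out is not given by arm and is not the same as stopping sessions, so using 15% for the latter is an assumption. Also assumed are an equal true 24-week risk p in both arms, a constant hazard, stopping at a time uniform over 24 weeks and unrelated to events, and recording only until the participant stops.

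- Cumulative hazard: H = −ln(1 − p).
- Mean recorded risk in those who stop: m = 1 − p/H.
- If a fraction q stops, the arm's recorded risk falls by q(p − m).

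For p = 0.20: H = 0.2231 and m = 1 − 0.20/0.2231 = 0.104. With q = 0.15 the loss is 0.15 × (0.200 − 0.104) = 0.014, or 0.9 of 62 participants.

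For p = 0.40: H = 0.5108 and m = 1 − 0.40/0.5108 = 0.217. With q = 0.15 the loss is 0.15 × (0.400 − 0.217) = 0.027, or 1.7 of 62.

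If nobody stops in the other arm, these losses are also the differences between arms: 1.4 and 2.7 points. With 30% against 0% they are 2.9 and 5.5 points (1.8 and 3.4 participants). If both arms lose the same fraction, the difference is zero, although both under-record. If the arms are swapped, the sign reverses.

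**The case against.** The strongest reply is that the rule names one query point without excluding others. That stands: *only stated* is as far as the text goes. The protocol also refers to an appendix with a week-by-week assessment table that is not in the text reviewed, and scripts may sit in a procedures manual. The investigator and study physician monitor safety overall, and frequent contact with people who meet barriers to participation is described. Informal questioning is therefore likely, but nothing in the text makes it systematic or the same in both arms.

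A reader might go further and infer that the arm comparison of adverse events is biased, with controls under-recorded because they are merely invited and need attend only 9 of 12 sessions. The documents do not support this, for four reasons:

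- The rule speaks of participants without limiting it to an arm. Table 2 codes the bi-weekly monitoring contact as the intervention contact, and Compliance and satisfaction has weight collected bi-weekly in both groups. On that reading attendance at the educational sessions is irrelevant.
- The 75% is a reward threshold, not expected attendance, and controls are the only arm with a stated attendance reward. The direction could go either way.
- A missed session can be made good at the next one, so fewer queries does not mean proportionally fewer recorded events. The loss falls mainly on those who stop altogether.
- Data analyses plans no between-arm test of adverse events.

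Two further points are fair. Lean and bone loss are measured by DXA, so of the Background's concerns clinical fracture is the one that most depends on reporting. And for people still attending sessions, a query at weeks 23 and 24 largely duplicates the session query.

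**Conclusion.** The gap holds in limited form. As written, a participant who stops sessions but still attends assessments is not scheduled to be asked about adverse events again, and the ambiguity over which control contact carries the query leaves equal ascertainment unsecured. It does not show that the safety comparison is biased, and no direction can be given.

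The effect is probably modest at 15% drop-out. The figures of 1 to 2 participants of 62 rest on assumed risks and on stopping being unrelated to events. If events themselves lead people to stop, the loss would be larger, and the documents give no means of sizing it. The finding also rests on the appendix schedule not already listing a query at the assessment visits. This is a low-priority point, worth making because the remedy is cheap.

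**What to change.** Revise the adverse event rule so that the same scripted question, covering the period since last contact, is asked in both arms:

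- at every bi-weekly weigh-in;
- at the week-12, week-23 and week-24 visits, including participants who have stopped sessions;
- by phone for participants who attend neither. Without this, those who leave altogether would still be missed.

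Add to Data analyses that adverse events are reported by arm for all randomised participants, together with the number of contacts at which the question was asked, so that a reader can judge whether ascertainment was equal. If the appendix already schedules such queries, the adverse event section should say so.

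The form exists and the visits already take place; the phone query is the one new contact. The cost is a few minutes of staff time per contact and somewhat more recorded events. The sample size and the primary analysis do not change.
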